If an institutional creatinine result is used to guide Ramipril titration, then the upper limit of normal of the institutional lab should be used to guide titration as described above. Either the local institutional lab or LabCorp lab should be chosen and used for all Week 1-6 visits to be consistent with the normal values used during the titration period. If choosing to use local institutional labs for Week 1-6 visits, please also draw and submit research LabCorp labs to allow for comparison across study sites.

After RT is completed, patients will have a monthly phone call by study staff to assess for symptoms, medicine changes, compliance and toxicity on post RT month 2 and 3. On post RT month 4 (Week 22), patients will have a face-to-face visit with study staff to assess for symptoms, medicine changes, compliance and toxicity. Ramipril treatment may be terminated early if intercurrent illness occurs that prevents further administration, unacceptable adverse events occur, the patient decides to withdraw from the study or if changes in the patient's condition occur to render the patient unacceptable for further treatment in the judgment of the investigator. Patients will be followed for 30-days post Ramipril treatment ending with a phone call and toxicity assessment on the last study visit 5-month post RT (Week 26).

**Chemoradiotherapy:** Chemoradiotherapy will be performed using the same protocol as the standard arm of the RTOG 0825 study. 60 Gy Total dose will be delivered to the contrast-enhanced volume + 2 cm CTV margin. The FLAIR or T2 volume will receive 46 Gy + 2.5 cm margin. Dose limitations to critical structures will also be identical. Temozolomide will be administered daily and continuously starting on day 1 of radiotherapy and be given for a maximum of 49 days at a dose of 75 mg/m^2. Adjuvant temozolomide will be administered 5 consecutive days on days 1-5 of a 28-day cycle for 6 cycles at a starting dose of 150 mg/m^2. As per standard practice and in the absence of myelosuppression with cycle #1, the dose of temozolomide will be titrated upward to 200mg/m^2/d for cycles #2-6. Dose adjustments

by the treating physician will be allowed as per standard practice outlined in the official product monograph.

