### **4.4 Recruitment and Retention Plan**

**4.4.1** Patients with newly diagnosed glioblastoma will be identified by a member of their medical or local research team at each participating Research Base NCORP site. They may review cancer registry and medical chart information to identify patients eligible for this protocol. Patients identified will be asked about their interest in participating in a study of the cognitive effects of chemoradiotherapy in clinic or by a letter from their physician informing them about the study, and indicating that a research team member will be calling to tell them more about the study. Patients identified and spoken to by the study team should be added to the Screening Log (Appendix C). Accrual is expected to be 4 patients per month. Targeted accrual should be met in approximately 20 months. A maximum of 75 patients will be enrolled on this trial. Patients found to be eligible will be followed for up to 7 months. After the 5 month post RT phone call, the patient is no longer followed and data is no longer collected from the patient.

**4.4.2** Patients who meet eligibility criteria will be invited to participate in this clinical trial of a drug to improve cognitive functioning. Eligible patients will be administered the informed consent form (ICF). Screening logs are to be submitted to Wake Forest NCORP Research Base at the end of each month.

**4.4.3** Patients who meet all eligibility criteria and sign the ICF will be scheduled for a face-to-face assessment session during which baseline measures will be collected; for some patients this will occur at the screening visit. A research nurse or similarly qualified and trained individual will administer the battery of cognitive tests and questionnaires. Socio-demographics and health status will also be collected.

**4.4.4** The WF NCORP Research Base currently has 43 participating NCORPs inclusive of 14 NCORP-MUs located in 42 states, the District of Columbia and two U.S. territories (Guam and Puerto Rico), in addition to Wake Forest Baptist Medical Center. We will recruit participants from all

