## 7.2 Study Visit Windows

Study Visit	Visit Window
Enrollment	n/a
Baseline	≤ 14 days after Enrollment
Titration of Drug (Week 1-3)	+/- 3 days
During RT (Week 4-5)	+/- 3 days
RT Completion (Week 6)	+/- 3 days
1-month Post RT (Week 10)	+/- 7 days
2- & 3- month post RT (Week 14 & 18) Phone calls	+/- 7 days
4- month post RT (Week 22)	+/- 7 days
5- month post RT (Week 26) Phone Call	+/- 7 days

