MRI/CT Brain: MRI Brain will be completed per standard of care at each study site. Sites are asked to provide MRI final reports with the specific visit form. As per section 4.1.7, patients who are unable to undergo MRI scanning should have CT brain scans done as per this schedule. Treating physician assessment of tumor response – i.e. response, progression or stable disease – will be captured for each completed imaging study.

Toxicity Assessments: Assessments by the study team will be done from Week 1 of RT and the start of Ramipril to 5-month post RT (end of study). This time period includes 30 days after treatment with Ramipril. Refer to section 6.2 for reported adverse events and risks when taking Ramipril.

Adverse Event Reporting: Refer to Section 10 of the protocol for specifics.

**Medication Diary:** Each patient is asked to fill in a Ramipril Medication diary and return it to the study team weekly during radiation therapy (weeks 1-6), and monthly on 1- and 4- month post RT visit. Since 2- and 3- month visits can be phone calls, the patient will need to mail back these diaries to the study team. Refer to Appendix D for a Ramipril Medication diary.

**Pill Count:** Patients will be asked to bring pill bottles to visit. Study team will count and record pills given, remaining and taken on the visit CRF.

**Ramipril Administration:** This study drug will be provided at no charge to patients for oral administration daily from Week 1 RT to post 4-month RT (Week 22). Study team will be required to order, distribute and inventory study drug. Refer to Sections 6.3 – 6.8 and for titration schedule 5.1.2 for details.

**Chemoradiation Summary:** At the RT Completion (Week 6) visit, a summary of the standard of care chemotherapy and radiation therapy will be gathered.

**Off Agent:** Use this form when a patient goes Off Agent either at the completion of study drug administration per protocol or at the time of early discontinuation. All study assessment should be continue to be completed, unless the patient is unwilling or withdraws consent. LabCorp samples do not need to be collected after the patient is Off Agent. Please use local labs to complete assessment information in REDCap.

**Off Study:** Use this form when a patient goes Off Study by either withdrawing consent or completing the study. This form serves as a way to track the patient status.

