#### 8.3.1 Off-Agent Criteria

Participants may stop taking study agent for one or more of the following reasons: completed the protocol-prescribed intervention, adverse event (AE) or serious adverse event (SAE), inadequate agent supply, refusal to continue with study procedures, the need for contraindicated concomitant medications, medical contraindication, disease progression, death or treating physician decision.

Date and reason off-agent should be documented on the Off Agent case report form. Reasons that are not specified on the form should be coded as 'Other' and a brief description provided. Patients who go off-agent must be followed for adverse events (AEs) for at least 30 days from their last treatment.

Note that participants who go off-agent should be encouraged to stay in the study and provide data at the regularly scheduled visits. Local NCORP site staff should complete the study assessment with the patient, especially the neurocognitive and PROs testing and toxicity assessments. LabCorp samples do not need to be collected once the patient is "Off Agent.". Local institutional labs can be used to assess the participant after they are off Ramipril.

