#### 8.3.2 Off-Study Criteria

Participants may go 'off-study' for one or more of the following reasons: the protocol intervention and any protocol-required follow-up period is completed, AE/SAE, lost to follow-up, refusal to continue with study procedures, the need for contraindicated concomitant medication, medical contraindication, disease progression, withdraw consent, death, determination of ineligibility (including screen failure), pregnancy, or treating physician decision.

Note that a participant is not automatically taken off-study if they refuse further treatment. In fact, these participants should be encouraged to remain in the study and provide data at their regularly scheduled visits. Date and reason off-study should be documented on the Off Study case report form. Reasons that are not specified on the form should be coded as 'Other' and a brief description provided.

A final evaluation of the participant should be performed when he/she withdraws from the study. If a patient decides to discontinue participation in study at any time prior to study completion, the entire battery of neurocognitive tests and forms should be administered, using the next Neurocognitive and PRO booklet they would have received as well as, all other items in the Schedule of Events (Section 7.1) for the visit.

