#### 10.4 Responsibilities of Local Sites for Expedited Reporting (CTEP-AERS)

Wake Forest NCORP affiliates and sub-affiliates (local sites) are required to notify the WF NCORP Research Base if a participant has an adverse event requiring expedited reporting by emailing [contact]. All SAEs that meet expedited reporting criteria defined in the reporting table below will be reported via CTEP-AERS, the Adverse Event Expedited Reporting System, accessed via the CTEP web site, <https://ctepcore.nci.nih.gov/ctepaers/security/login>.

**IMPORTANT:** When reporting in CTEP-AERS please ensure a copy of the report is sent to WF NCORP RB by adding [[contact]](mailto:[contact]) to the distribution list within the reporting system.

Any correspondence between CTEP-AERS and/or the FDA about a reportable SAE should be forwarded to [[contact]](mailto:[contact]) also.

Commercial reporting requirements are provided in the table below. The commercial agent used in this study is Ramipril (Altace®).

**Expedited reporting requirements for adverse events experienced by participants who are receiving study agent/intervention (including within 30 days of the last administration of commercial study agent/intervention) should be reported as follows:**

Attribution	Grade 4		Grade 5	
	Expected	Unexpected	Expected	Unexpected
Unrelated or Unlikely			CTEP-AERS	CTEP-AERS
Possible, Probable, Definite		CTEP-AERS	CTEP-AERS	CTEP-AERS

1) This includes all deaths within 30 days of the last dose of study agent with a commercial agent/intervention, regardless of attribution. Any death that occurs more than 30 days after the last dose of study commercial agent/intervention and is attributed (possibly, probably or definitely) to the agent/intervention and is not due to cancer recurrence must be reported according to the instructions above.
 
2) Submission of the on-line CTEP-AERS report plus any necessary amendments generally completes the reporting requirements. You may, however, be asked to submit supporting clinical data to the CTEP-AERS, CIRB or WF NCORP RB in order to complete the evaluation of the event.
				

For more information see:

[https://ctep.cancer.gov/protocolDevelopment/electronic\\_applications/docs/aeguidelines.pdf](https://ctep.cancer.gov/protocolDevelopment/electronic_applications/docs/aeguidelines.pdf)

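### The closing safety call at Week 26 falls nominally 28 days after ramipril ends at Week 22, so the protocol's own 30-day follow-up is attainable but not assured

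*Combined protocol and SAP*

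**What the plan says.** Four places in the protocol rest on 30 days after the last dose:

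- Section 3 (Summary of Study Plan): "Patients will be followed for 30-days post Ramipril treatment ending with a phone call and toxicity assessment". It places this at the last study contact, 5 months post RT (Week 26).
- Section 7.3, on toxicity assessments up to 5 months post RT: "This time period includes 30 days after treatment with Ramipril".
- Section 8.3.1: "Patients who go off-agent must be followed for adverse events (AEs) for at least 30 days from their last treatment".
- Section 10.4, in the notes to the expedited reporting table, on what must be reported regardless of attribution: "This includes all deaths within 30 days of the last dose of study agent".

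The schedule is set elsewhere. Sections 7.3, 7.4 and 7.5 end ramipril at 4 months post RT (Week 22), and Section 7.5 has the Off Agent form completed at that visit. Section 5.2 places the final toxicity assessment, by phone, at Week 26. Section 7.2 gives +/- 7 days both to the Week 22 visit and to the "5- month post RT (Week 26) Phone Call". Section 4.4.1 closes follow-up there: "After the 5 month post RT phone call, the patient is no longer followed and data is no longer collected from the patient".

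**The concern.** The stated 30 days and the scheduled 28 days cannot both be right. A site that follows the calendar exactly falls short of Section 8.3.1. Nothing ties the call to the date of the actual last dose, so the visit windows can shorten or lengthen the interval without any departure from Section 7.2.

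At stake is the completeness of safety capture at the end of treatment. The duty to report deaths up to day 30 can outlast the last scheduled contact. The post-treatment observation time behind the toxicity summary in Section 12.7 also differs between patients for reasons unrelated to safety. The events concerned are those that Section 10.3 makes reportable: unexpected grade 3 events at least possibly related to the drug, unexpected grade 4 events, and all grade 5 events.

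**Working it through.** **Inputs.** Last dose at Week 22 (Sections 7.3 to 7.5). Closing call at Week 26 (Sections 3, 5.2, 7.1). Window of +/- 7 days on each contact (Section 7.2). Requirement of at least 30 days (Section 8.3.1). Drug supply (Section 6.6).

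**1. Can the 30 days be reproduced?** Not from the week numbers: (26 - 22) x 7 = 28 days, a shortfall of 30 - 28 = 2 days.

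**2. Does a month mean four weeks here?** Yes. Section 8.1 equates 4 weeks with 1 month post RT, and the visit labels follow that rule: 6 + 4 = 10, 6 + 16 = 22, 6 + 20 = 26. The drug supply agrees:
- First shipment: 7 x 1 + 7 x 2 + 28 x 4 = 133 capsules, which covers 42 days.
- Second shipment: 4 x 112 = 448 capsules; 448 / 4 = 112 days at four capsules a day.
- Total: 42 + 112 = 154 days = 22 weeks exactly.

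True calendar months would put 28 to 31 days (mean 30.4) between the two contacts. They would also place those contacts at about Weeks 23.4 and 27.7, which contradicts the stated Weeks 22 and 26.

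**3. Effect of the windows.**

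| Assumption | Days from last dose to call | Largest shortfall against 30 |
|---|---|---|
| Both contacts exactly on schedule | 28 | 2 |
| Last dose at nominal Week 22, call +/- 7 | 28 - 7 = 21 to 28 + 7 = 35 | 9 |
| Last dose moves with the Week 22 visit, both +/- 7 | 28 - 14 = 14 to 28 + 14 = 42 | 16 |

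In the second row, 28 + b >= 30 needs b >= 2. That is +2 to +7 days, or 6 of the 15 permitted call days. In the third row, 91 of the 15 x 15 = 225 day combinations (40%) give 30 days or more. This counts what the windows permit. It does not forecast what sites will do.

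**4. How plausible is the 14-day end?** It needs a Week 22 visit 7 days late, dosing continued to that visit, and a call 7 days early. At full dose with no missed doses the supply runs out at day 154, so dosing past Week 22 needs leftover capsules from missed doses or a lower dose.

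**5. Illustration of size.** The assumptions are a constant death hazard, the 16.0-month median survival that Section 3 quotes for temozolomide alone, and all 75 patients on drug at Week 22. The probability of death in 2 days is then 1 - 0.5^(2 / (16 x 30.44)) = 0.28%, or 0.2 deaths among 75. Fewer patients on drug at Week 22 would lower this. The planning retention at Week 10 is already only 65% to 80% (Section 12.2).

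**The case against.** The strongest reply is that this is a 2-day labelling slip. The call window lets a site satisfy Sections 7.2 and 8.3.1 together, and Section 8.3.1 binds whatever the visit table says. Section 10.4 requires deaths within 30 days to be reported independently of the call. Six 28-day cycles of adjuvant temozolomide run 168 days (24 weeks), whereas Week 26 is 20 weeks after RT, so many patients are still under the site's care. Patients who stop early and stay on study to Week 26 have longer follow-up, not shorter.

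Most of that stands, and it rules out several stronger readings that a reader might infer:

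- **That 30 days of follow-up is never delivered.** The permitted range extends to 35 or 42 days, so 30 days can be reached.
- **That closing a patient out at 14 days is fully compliant.** It meets Section 7.2 but breaches Section 8.3.1.
- **That deaths in the missed days go unascertained.** The reporting duty in Section 10.4 does not depend on the call. What can be said is that no scheduled contact asks about those days, while Section 4.4.1 ends data collection.
- **That Section 8.3.2 contradicts Section 8.3.1.** Its sentence "A final evaluation of the participant should be performed when he/she withdraws from the study" waives nothing. A treated patient who leaves the study has also gone off agent, so the 30-day rule still applies. What is missing is a cross-reference.
- **That one or two deaths would be missed.** The step 5 formula at 16 days gives 2.25%, or 1.7 of 75, but only if all 75 patients are on drug at Week 22 and all sit at the extreme of both windows.

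The reply does not remove the mismatch itself: a patient handled exactly on the printed schedule does not get the follow-up that the protocol says it provides.

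**Conclusion.** The inconsistency is real and minor. On the protocol's own week numbers, follow-up after the last dose is 28 days against a requirement of at least 30, and the windows make 30 days attainable but not assured. The 2-day figure rests only on the Week 22 and Week 26 labels. The 21-to-35-day range also assumes that dosing ends at nominal Week 22. The 14-to-42-day range assumes that dosing follows the visit, as Section 7.5 allows, with leftover capsules needed at the low end. The retention and neurocognitive endpoints at Week 10 are not touched.

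A related mismatch should be settled at the same time. In Section 7.1, as the table reads in the extracted text, the Toxicity Assessment row is marked only through Week 10, while Section 7.3 runs these assessments to 5 months post RT.

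**What to change.** 1. In Sections 7.1, 7.2 and 7.3, time the closing safety call no earlier than 30 days after the actual last ramipril dose, with a one-sided window (for example day 30 to day 37). Match the wording in Sections 3 and 5.2 and in Appendix B.
2. For patients who stop ramipril early, keep every scheduled assessment. In Section 4.4.1, end data collection at the later of the Week 26 contact and the 30-day contact. Ending it at a call tied only to an early last dose would close patients out before the Week 10 and Week 22 batteries, contrary to Sections 7.3 and 8.3.1.
3. In Section 8.3.2, add a cross-reference saying that the Section 8.3.1 follow-up still applies to treated patients who leave the study without withdrawing consent.
4. Reconcile the Toxicity Assessment row in Section 7.1 with Section 7.3.
5. Reconcile the total follow-up, which Section 2.3 limits to 6 months and Section 4.4.1 to 7 months. A call 30 days after day 154 falls on day 184 or later.

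This changes no dose, treatment duration or stopping rule; it makes the schedule meet a rule the protocol already has. The cost is wording in several sections and a few days' longer follow-up per patient. The phone call itself already exists, and for early leavers the contact is what Section 8.3.1 already implies.

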#### **Cognitive & PRO Testing:**

**Participant Related Outcomes Assessments (PRO) (EORTCLQ-30/BN20):** Study Team should administer at Baseline, RT Completion, 1- and 4- month post RT visits. *If patient goes Off-Study for any reason, the PRO should be administered.*

**Neurocognitive Assessments (HVLt-R, Trail Making Tests, Part A & B, COWAT and Shipley Institute of Living Scale):** The entire battery of neurocognitive tests and questionnaires will be administered by a trained and certified examiner. Refer to Section 7.6 for specifics. Note that the Shipley Institute of Living Scale will only be given at Baseline, while all others are also given at RT Completion, 1- and 4- Post RT visits. *If patient goes Off-Study for any reason, the entire next set of Neurocognitive Assessments should be administered, except the Shipley Institute of Living Scale.*

## **7.4 Study Agent - Ramipril**

Study agent Ramipril will be given from Week 1 of RT until 4 months post RT (Week 22). A titration period will be during weeks 1-3 of RT to determine the maximum dose, which will be continued until 4 months post RT (Week 22).

Refer to the following sections for details as needed:

- Section 5.1 Dose Regimen
- Section 5.2 Administration, including titration period
- Section 5.3 Contraindications
- Section 5.4 Concomitant Medications
- Section 5.5 Dose Modifications

- Section 5.6 Adherence/Compliance

## 7.5 Evaluation at Completion of Study Intervention

The study agent Ramipril will be discontinued at 4 months post radiation therapy or, prematurely, if any of the Off-Agent criteria are met (refer to section 8.3). At this visit the study team should complete the Off Agent form and any other forms required for the visit.

## 7.6 Methods for Neurocognitive & Participant Related Outcomes Tests

### 7.6.1 Specific Training and Certification Procedures

Each participating site will be required to have at least one examiner who is trained and certified in the administration and scoring of the cognitive battery (neurocognitive tests and questionnaires). Training will follow the procedures developed in prior WF NCORP neurocognitive studies such as our recently completed Phase II feasibility study trial of donepezil in breast cancer survivors previously exposed to chemotherapy. We will train using didactic presentations (describing the purpose and instructions for each test and questionnaire), live and video demonstrations of a complete battery administration, live practice sessions supervised by a certified examiner and trainer with specific feedback, and a review by certified trainers of an audio-recorded administration. If needed, remediation will occur with review of subsequent recorded administrations with corrective feedback. Once the examiner has met study criteria s/he will be certified to administer and score the battery at his/her site. Periodic re-certifications will be required. If an examiner has been trained and certified previously by WF NCORP RB and has administered all of the neurocognitive tests required in this protocol within the last 12 months, they will only need to participate in an abbreviated training. This procedure has been successfully used in our studies of cognitive effects of cancer and its treatments as well as by [name] and his team in large scale, multi-site clinical trials and observational studies (e.g., WHIMS, CoSTAR, SPRINT, Look AHEAD, LIFE, MESA).

